7.5. Prohibitions and Restrictions

Potential patients must be willing and able to adhere to the following prohibitions and restrictions during the course of the study to be eligible for participation:

1. Refer to [Section 9](#), Concomitant Medications, for details regarding prohibited and restricted therapy during the study.
2. Agree to follow all requirements that must be met during the study as noted in the Inclusion and Exclusion Criteria (e.g., contraceptive requirements).

3. If patients need to be outdoors while on the study, they should wear clothes that protect skin from sun exposure, such as a long-sleeved shirt, and also a wide-brimmed hat and sunglasses. Patients should discuss other sun protection measures with their physician.

8. STUDY DRUG INFORMATION

8.1. Description of TRC253 Capsules

The TRC253 supplied for this study is formulated as oral capsules with a strength of 10 mg, 40 mg, and 100 mg. The 10 mg capsules will be gray in color. The 40 mg capsules will be white in color. The 100 mg capsules will be red in color. It will be manufactured and provided under the responsibility of the sponsor.

8.2. TRC253 Packaging and Labeling

The study drug will be packaged in high-density polyethylene bottles with child-resistant closures.

Study drug labels will contain information to meet the applicable regulatory requirements.

8.3. TRC253 Handling, and Storage

The study drugs must be stored at controlled room temperature in a secure area and administered only to patients enrolled in the clinical study in accordance with the conditions specified in this protocol.

Refer to the pharmacy manual for additional guidance on study drug handling and storage.

8.4. TRC253 Dose Levels

Table 9: Dose Levels

Cohort	TRC253 Dose Levels	Number of Evaluable Patients
Phase 1		
1	40 mg	Up to 6
2	80 mg	Up to 6
3	160 mg	Up to 6
4	240 mg	Up to 6
5	280 mg	Up to 6
6	320 mg	Up to 6
Phase 2		
F877L Mutation cohort	280 mg	Up to 15
Lack of F877L or sole L702H Mutation cohort	280 mg	Up to 30
Sole L702H Mutation cohort	280 mg	Up to 15

During Part 1 of the study, patients will be assigned sequentially to increasing TRC253 doses. The starting dose of TRC253 is 40 mg once daily in the morning, orally. TRC253 doses will be escalated in subsequent cohorts after all patients enrolled in a given cohort have completed the 28-day DLT evaluation period. Dose escalation in Part 1 will follow single-patient dose escalation design until drug-related toxicity occurs per [Table 4](#). When an initial drug-related toxicity occurs per [Table 4](#) or DLT per [Table 6](#) in a single patient the cohort will be expanded

according to 3+3 design rules. Any single patient cohort may be expanded to include additional patients for purposes of collecting additional PK, PD (FDHT-PET), and PSA response data to help inform selection of a MED.

Subsequent dose levels will enroll patients based on 3+3 design, whereby 3 patients will be initially enrolled and treated at each dose level. If none of these 3 patients experiences a dose-limiting toxicity (DLT) during the initial 28-day evaluation period, the dose level will be expanded to 6 patients. The MTD will have been exceeded if $\geq 33\%$ of patients experience DLT at a given dose level. DLT will have occurred when a patient has 1 or more toxicity listed in

[Table 6](#) that is at least possibly related to TRC253 during the first 28 days of dosing. Patients who exit the study for reasons other than DLT prior to completion of the 28-day DLT evaluation period will be replaced to ensure an adequate safety assessment in each cohort. Patients who experience DLT who receive less than the prescribed dose of TRC253 due to documented toxicity during the DLT evaluation period will be considered evaluable for dose escalation purposes. At the MTD or MED, up to twelve patients may be enrolled prior to confirming the RP2D. Dose escalation will take into account all available data including PK/PD data and the safety profile of prior cohorts, as evaluated by medical monitor and Principal Investigators.

Part 2 will consist of three cohorts of initially up to 15 patients (Cohort 1), up to 30 patients (Cohort 2), and up to 15 patients (Cohort 3) to receive TRC253 at the RP2D of 280 mg. The objective of Part 2 is to gather additional information on the safety, PK and PD characteristics, and the clinical efficacy of TRC253 in a pre-defined population of patients with metastatic CRPC. Patients enrolled into Part 2 will have received prior treatment with enzalutamide or apalutamide. Patients will be centrally screened for the presence of the AR F877L and AR L702H mutations from a plasma sample and enrolled into Cohort 1 (AR F877L positive), Cohort 2 (patients without AR F877L and without sole AR L702H mutations), or Cohort 3 (sole AR L702H mutation positive).

Patients may be moved from a lower to a higher TRC253 dose not exceeding the MTD or MED once it has been deemed safe by the medical monitor and Principal Investigators.

8.5. TRC253 Dosage and Administration

TRC253 will be administered orally once daily in the morning in 28-day cycles. However, in Part 1, a single dose of TRC253 will be taken on the first day (i.e., Cycle 1 Day 1) of a 7-day cycle. During Cycle 1, the pharmacokinetic characteristics of a single dose of TRC253 will be investigated. Starting with treatment Cycle 2 Day 1, TRC253 will be taken once daily in the morning. The original proposed TRC253 doses were 40 mg, 80 mg, 160 mg, 240 mg, 320 mg, and 400 mg; and intermediate dose levels could be implemented based on safety, tolerability, PK, PD and other observations at each dose level following review of data with the principal investigators at all treating sites.

While the maximum tolerated dose was not reached, PK exposures at the 320 mg dose level significantly exceeded the target efficacious concentration and a decision was made not to proceed to 400 mg. Based on review of PK and safety, the RP2D of 280 mg was chosen.

In Part 2, TRC253 capsules are taken once daily in the morning starting on Cycle 1 Day 1 at the MTD or MED.

On extended PK days, no food should be consumed for at least 8 hours before and 4 hours following TRC253 dosing. On all other days, no food should be consumed for at least 2 hours before and 1 hour after dosing.

Study-site personnel will instruct patients on how to store study drug for at-home use as indicated for this protocol.

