12. Major surgery (e.g., requiring general anesthesia) within 3 weeks before screening, or has not fully recovered from prior surgery (i.e., unhealed wound), or surgery planned during the time the patient is expected to participate in the study. **Note:** patients with planned surgical procedures to be conducted under local anesthesia may participate.
13. Plan to father a child while enrolled in this study or within 90 days after the last dose of study drug.
14. Pre-existing chronic hypokalemia or hypomagnesemia.

NOTE: Investigators should ensure that all study enrollment criteria have been met at screening. If a patient's status changes (including laboratory results or receipt of additional medical records) after screening but before the first dose of study drug is given such that he no longer meets all eligibility criteria, supportive treatment may be administered, if necessary, so that eligibility criteria can be met and laboratory test(s) may be repeated once, to determine if the patient qualifies for the study. If enrollment criteria are not met after further evaluation, then the patient should be excluded from participation in the study.

Dosage and Administration

Part 1: a single dose of TRC253 will be taken on the first day (i.e., Cycle 1 Day 1) of a 7-day cycle. During Cycle 1, the pharmacokinetic characteristics of a single dose of TRC253 will be investigated.

TRC253 will be administered orally once daily in the morning in 28-day cycles starting in Cycle 2. Starting with treatment Cycle 2 Day 1, TRC253 will be taken once daily in the morning. The proposed TRC253 doses are 40 mg, 80 mg, 160 mg, 240 mg, 320 mg, and 400 mg; however, intermediate dose levels may be implemented based on safety, tolerability, PK, PD and other observations at each dose level following review of data with the principal investigators at all treating sites.

Part 2: TRC253 capsules are taken once daily in the morning starting on Cycle 1 Day 1 at the MTD or MED in 28-day cycles.

On extended PK days, no food should be consumed for at least 8 hours before and 4 hours following TRC253 dosing. On all other days, no food should be consumed for at least 2 hours before and 1 hour after dosing.

Withdrawal Criteria:

Patients will be withdrawn from study treatment if, in the opinion of the Investigator, it is medically necessary, or if it is the wish of the patient. In addition, patients will be withdrawn from treatment for any of the following reasons:

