2.4. Phase 1 and Phase 2 253PC101 Ongoing Study Results

Twenty-two patients participated in the dose escalation portion of the study and initially enrolled at TRC253 doses of 40 (n=1), 80 (n=1), 160 (n=2), 240 (n=6), 280 (n=2), and 320 mg (n=10) and 12 have enrolled in the expansion portion. Although only 2 patients initially enrolled at 280 mg, 1 patient initially dosed at 240 mg dose escalated to 280 mg and 2 patients dosed at 320 mg dose reduced to 280 mg after the first dose; thus, a total of patients were evaluated at 280 mg prior to determination of the RP2D. There were no deaths, no drug-related serious adverse events (SAEs), and no grade 4 adverse events (AEs).

The maximum tolerated dose was not reached. However, the single DLT observed in the study of grade 3 QTcF prolongation occurred at the 320 mg dose level and steady state drug exposure at the 320 mg dose level significantly exceeded the target concentration. Therefore, dose escalation did not proceed to the 400 mg dose level and the 280 mg dose level was explored and declared the RP2D based on the lack of DLT and consistent steady state exposures above the target concentration. In general, TRC253 has been well-tolerated. Three patients discontinued due to AEs: 1 patient discontinued due to spinal cord compression secondary to disease progression, and 2 patients discontinued due to QTcF prolongation, both of which were suspected related to TRC253. Prolongation of QTcF of grade 1 or 2 severity has been seen in the majority of patients and requires serial monitoring of ECGs.

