- The proposed TRC253 doses are 40 mg, 80 mg, 160 mg, 240 mg, 320 mg, and 400 mg; however, intermediate dose levels may be implemented based on safety, tolerability, PK, PD and other observations at each dose level with consent of the medical monitor and Principal Investigators. Escalation to the next dose level will occur with consent of the medical monitor and treating Principal Investigators following review of safety, tolerability, PD and other observations at previous dose levels.
- Intra-patient dose escalation is allowed. A patient may dose escalate to a dose level at or below the maximum tolerated dose (MTD) if (1) the new dose level has been declared safe by the medical monitor and Principal Investigators, (2) the medical monitor has been consulted, (3) the disease has not progressed, and (4) the patient has completed three 28-day cycles of treatment at a given dose level (multiple dose escalations are permitted).

The MTD, maximum administered dose (MAD), minimum efficacious dose (MED), and RP2D are defined as follows:

- Maximum-tolerated Dose: MTD is the highest TRC253 dose at which the probability of DLT is < 33% (or < 2 out of 6).
- Maximum-administered Dose: MAD is the highest TRC253 dose administered in case the MTD cannot be defined.
- Minimum Efficacious Dose: MED is defined as the lowest TRC253 dose administered at which PK, mean plasma trough concentration (C_{trough}) > 335 ng/mL (623 nM) with demonstrable PD and efficacy data. In addition, data from FDHT-PET scans may be used to confirm the MED.
- Recommended Phase 2 Dose: RP2D will be equal to or below the MTD (or the MAD) and the MED. A lower dose of TRC253 may be selected as the RP2D on the basis of cumulative safety, PK, PD, and efficacy data.

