8.5.2. TRC253 Dose Modification/Dose Interruptions

The phase 2 dose of TRC253 is 280 mg daily.

Dose modifications and/or dose interruptions may be warranted for patients who experience toxicities. Patients with toxicities that are manageable with supportive care (i.e., nausea or vomiting) may not warrant dose reduction. For any occurrence of grade 2 or greater non-hematologic toxicity, study drug may be held until toxicities have resolved or improved to grade 1 or baseline, then resume drug at the same dose if the event was a tolerable grade 2 (at PI's discretion). Dose interruption or reduction to 240 mg is also permitted for grade 2 toxicity at the discretion of the investigator. If the event is grade 3 or 4, the study drug dose should be reduced to 240 mg when resuming drug administration. For a subsequent episode of a grade 3 adverse event, dose reduction to 200 mg is warranted once patient has recovered. If there is no recovery to \leq grade 1 or baseline after a 21 day delay, the patient should be discontinued from the study.

Dose modifications or interruptions may be necessary for liver enzyme elevations. For grade 2 aspartate aminotransferase (AST) or alanine aminotransferase (ALT) elevation (>3 times to <5 times the upper limit of normal), without signs of severe liver damage, stop study drug until liver enzymes return to baseline values. Once liver enzymes have returned to baseline values, treatment may be reintroduced at 240 mg. Discontinue study drug for AST or ALT elevations $>5X$ ULN or for patients who meet Hy's Law criteria (concurrent elevation of AST or ALT $>3X$ ULN and total bilirubin $>2X$ ULN).

Dosage modification or treatment interruptions may also be necessary for patients with diarrhea or nausea/vomiting. Treat diarrhea at first signs with adequate hydration and antidiarrheal medication (e.g., loperamide), and consider treatment interruption if diarrhea continues. For grade ≥ 3 adverse events, first episode, patient should hold TRC253 until \leq grade 1 or baseline, then may restart at 240 mg. After a second episode of a grade 3 adverse event, further dose reduction to 200 mg is warranted once patient has recovered. If no recovery to \leq grade 1 or baseline after a 21 day delay, the patient should be discontinued from the study.

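### Part 2 dosing and the intra-patient escalation ceiling still refer to the MTD or MED, which name no identifiable dose beside the declared 280 mg, and the ceiling is worded in two different ways

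*Combined protocol and SAP*

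**What the plan says.** **Part 2 dose.** Section 8.5 states: "In Part 2, TRC253 capsules are taken once daily in the morning starting on Cycle 1 Day 1 at the MTD or MED". The Dosage and Administration part of the Synopsis has the same instruction: "TRC253 capsules are taken once daily in the morning starting on Cycle 1 Day 1 at the MTD or MED in 28-day cycles". Elsewhere the dose is a number. Section 8.4 enrols the three cohorts "to receive TRC253 at the RP2D of 280 mg", Section 5.1.2 gives 280 mg for each cohort, Table 9 lists it for every Phase 2 cohort, and Section 8.5.2 says "The phase 2 dose of TRC253 is 280 mg daily".

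**Status of the MTD.** Section 2.4: "The maximum tolerated dose was not reached". Section 8.5, shortly before the Part 2 instruction: "While the maximum tolerated dose was not reached, PK exposures at the 320 mg dose level significantly exceeded the target efficacious concentration". The 400 mg level was not opened.

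**Ceiling on raising a patient's dose.** Section 5.1.1 (Part 1): "A patient may dose escalate to a dose level at or below the maximum tolerated dose (MTD". Section 8.4, directly after its Part 2 paragraph and with no restriction to either part: "Patients may be moved from a lower to a higher TRC253 dose not exceeding the MTD or MED".

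**Definitions (Section 5.1.1).** The MTD is the highest dose with a DLT probability under 33% (fewer than 2 of 6). The MAD is the highest dose given if no MTD can be defined. The MED is the lowest dose with a mean trough above 335 ng/mL plus demonstrable PD and efficacy. The RP2D is at or below the MTD (or MAD) and the MED, and may be set lower.

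**The concern.** Section 8.5 reports that no MTD was reached, gives the chosen dose, and then directs Part 2 dosing to a level identified only by the MTD or the MED. The same section had already been updated for the end of escalation, since it describes the planned dose levels in the past tense. The Part 2 instruction therefore looks like escalation-phase wording that survived the revision.

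The escalation ceiling matters more. It is a safety limit in current text, stated in two ways and tied in both to a quantity the protocol says was not reached. The provision has been used: Section 2.4 reports one patient raised from 240 mg to 280 mg. The only DLT was at 320 mg, the level directly above 280 mg in Table 9, where exposure was well above target. On the analysis side, Section 14.4.3 summarises ECG changes by dose group and cohort, and Section 14.8 allows Part 1 patients on the same dose to be combined with Part 2. If Part 2 patients could move above 280 mg, later ECG and efficacy data in a cohort would no longer describe 280 mg alone.

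**Working it through.** No figure in the plan depends on this point, so the check is a side-by-side reading with a little arithmetic.

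1. **Is the MTD-or-MED phrase another way of saying 280 mg?** Section 2.4 calls 280 mg only the RP2D, chosen for lack of DLT and exposures above target. It does not say that this was the lowest such dose, which the MED definition requires. The RP2D may also lie below both the MTD and the MED. The phrase is therefore not a synonym for 280 mg, although the two could coincide if 280 mg is the MED.

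2. **What could the MTD term point to?** As reported, nothing, because it was not reached. Read literally, the definition could point to 320 mg. Section 2.4 gives one DLT, at 320 mg, with 10 patients initially enrolled there: 1/10 = 10%, exact 95% interval 0.3% to 44.5%, assuming all 10 were evaluable. Two patients dosed at 320 mg were reduced to 280 mg after the first dose; without them the rate is 1/8 = 12.5%. Both point estimates are below 33%, although the interval for 1/10 extends above it. The literal reading and the reported status differ.

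3. **What could the MED term point to?** The available text gives a criterion but no dose, and two passages pull apart:
   - Section 5.4 projected 65 mg daily to reach 335 ng/mL. The first planned level above that is 80 mg, and 280/65 = 4.3. This is a pre-study projection, not observed trough data, and covers only the exposure part of the criterion.
   - The RP2D rule in Section 5.1.1 puts the RP2D at or below the MED. With an RP2D of 280 mg, the MED is at least 280 mg.

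   The text does not settle which holds.

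4. **Is the MAD used?** It is defined for exactly this situation, and 320 mg is the highest level in Table 9. Neither ceiling sentence refers to it.

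5. **Do the two ceilings agree?**

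| | Section 5.1.1 | Section 8.4 |
|---|---|---|
| Limit | MTD | MTD or MED |
| Dose in mg | none | none |
| Scope | within the Part 1 section | unrestricted, follows the Part 2 paragraph |
| Other conditions | level judged safe, medical monitor consulted, no progression, three 28-day cycles completed | level judged safe |

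They differ in limit, scope and conditions.

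6. **When could Part 2 data be touched?** If the three-cycle condition applies, 3 × 28 = 84 days = 12 weeks, so escalation would not be expected to precede the Week 12 PSA. The confirmatory PSA at least 4 weeks later (Section 14.3), time to PSA progression, rPFS and later ECGs could be affected. Section 8.4 does not repeat the three-cycle condition.

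**The case against.** The strongest reply is that the Part 2 dose is not in doubt. It is stated as 280 mg many times, including in Section 8.5 just before the sentence at issue, and the reductions to 240 mg and 200 mg in Sections 8.5.2 and 8.5.3 start from it. That stands: it is hard to see a site starting a Part 2 patient at another dose.

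A reader might go further in four ways that the documents do not support.

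- *That the plan never states the MED.* It is defined by criterion. The pharmacokinetic results subsection (2.4.3) was not available to this review, so a dose may be named there.
- *That escalation has no upper limit.* The new level must have been judged safe, Section 5.1.1 adds three further conditions, 400 mg was not opened, and 320 mg tops Table 9.
- *That the MED ceiling could fall below 280 mg, so that the two ceilings point in opposite directions.* The RP2D rule in Section 5.1.1 weighs against this. The ceilings differ and are unresolved; nothing more is shown.
- *That QTcF prolongation in 22 of 34 patients (65%) measures the problem.* That figure pools both parts and all doses and says nothing about the ceiling.

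It can also be said that the Section 5.1.1 rule belongs to Part 1 and that the available text reports no Part 2 escalation. Both are fair. But the Section 8.4 sentence is not confined to Part 1, and whether it governs Part 2 is one of the things left open.

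**Conclusion.** The point holds as an internal inconsistency in current dosing text. For the Part 2 starting dose it is leftover wording with little practical effect. For intra-patient escalation it is a safety limit expressed in two ways, neither resolving to a dose in the available text and neither using the MAD fallback.

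Its size cannot be given as a bias or an error rate. The clinical stake is that the single DLT was at 320 mg, above the Part 2 dose. The analytical stake is limited to cohort and by-dose summaries after any escalation, and under the three-cycle condition mainly to data after Week 12.

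The conclusion assumes that no MED dose is given in the results text that was not available. If 280 mg is named there as the MED, the Part 2 instruction could be read consistently, but the mismatch between Sections 5.1.1 and 8.4 would remain. The change should be made; it does not call the design into question.

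**What to change.** Reconcile the Part 2 instruction in Section 8.5 and in the Synopsis with the Part 2 dose declared in Sections 5.1.2 and 8.5.2. Reconcile the escalation sentences in Sections 5.1.1 and 8.4 so that one identifiable limit applies with one set of conditions, and state whether it applies in Part 2. If the limit is expressed through the MTD, MED or MAD, name the dose that term denotes. The sponsor must decide the limit; none is proposed here.

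The cost is wording in four places of one amendment, with no change to sample size, the assessment schedule or the planned analyses.

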8.5.1. TRC253 Missed Doses

If a dose is missed in the morning, the patient may take the dose by 10 PM on the same day. Otherwise, the patient should resume dosing the next day. There should be at least 8 hours between doses.

8.5.2. TRC253 Dose Modification/Dose Interruptions

The phase 2 dose of TRC253 is 280 mg daily.

Dose modifications and/or dose interruptions may be warranted for patients who experience toxicities. Patients with toxicities that are manageable with supportive care (i.e., nausea or vomiting) may not warrant dose reduction. For any occurrence of grade 2 or greater non-hematologic toxicity, study drug may be held until toxicities have resolved or improved to grade 1 or baseline, then resume drug at the same dose if the event was a tolerable grade 2 (at PI's discretion). Dose interruption or reduction to 240 mg is also permitted for grade 2 toxicity at the discretion of the investigator. If the event is grade 3 or 4, the study drug dose should be reduced to 240 mg when resuming drug administration. For a subsequent episode of a grade 3 adverse event, dose reduction to 200 mg is warranted once patient has recovered. If there is no recovery to \leq grade 1 or baseline after a 21 day delay, the patient should be discontinued from the study.

Dose modifications or interruptions may be necessary for liver enzyme elevations. For grade 2 aspartate aminotransferase (AST) or alanine aminotransferase (ALT) elevation (>3 times to <5 times the upper limit of normal), without signs of severe liver damage, stop study drug until liver enzymes return to baseline values. Once liver enzymes have returned to baseline values, treatment may be reintroduced at 240 mg. Discontinue study drug for AST or ALT elevations $>5X$ ULN or for patients who meet Hy's Law criteria (concurrent elevation of AST or ALT $>3X$ ULN and total bilirubin $>2X$ ULN).

Dosage modification or treatment interruptions may also be necessary for patients with diarrhea or nausea/vomiting. Treat diarrhea at first signs with adequate hydration and antidiarrheal medication (e.g., loperamide), and consider treatment interruption if diarrhea continues. For grade ≥ 3 adverse events, first episode, patient should hold TRC253 until \leq grade 1 or baseline, then may restart at 240 mg. After a second episode of a grade 3 adverse event, further dose reduction to 200 mg is warranted once patient has recovered. If no recovery to \leq grade 1 or baseline after a 21 day delay, the patient should be discontinued from the study.

Nausea or vomiting should be treated with supportive care including anti-emetic therapy and, if persistent, may require treatment interruption or dose reduction. For grade ≥ 3 adverse events, first episode- patient should hold TRC253 until \leq grade 1 or baseline, then may restart at 240 mg. After a second episode of a grade 3 adverse event, dose further dose reduction to 200 mg is warranted once patient has recovered. If no recovery to \leq grade 1 or baseline after a 21 day delay, patient should be discontinued from the study.

Further dose reductions below 200 mg may be permitted following discussion with the Sponsor.

Additionally, in Part 2, patients should be considered for dose reduction if they experience toxicities outlined in [Table 6](#).

Dose interruptions are allowed for a maximum of 21 days; if dosing is not restarted in that time frame, the patient should be discontinued from the study.

